We also estimated statistical power for STD incidence specifically. Some of the participants will be sexually experienced at the time of the follow-ups and therefore at risk of STD, but others will not be sexually experienced and therefore not at risk for STD. The power analysis for STD incidence must take into account the size of sample that is at risk. The median age of first sexual intercourse in South Africa is about 16 (MacPhail et al., 2002; Manzini, 2001; Richter et al., 2005; Simbayi et al., 2004). At baseline 76.54% of the adolescents in our study were 12 years or older and therefore will be 16 years or older at the 54-month follow-up. We considered three different rates of sexual experience and risk for STD at the 54-month follow-up: 76.5% (N=809), 51.3% (N=542), and 38.3% (N=405) of the original 1,057 participants.

Based on previous studies (Auvert et al., 2001; Johnson et al., 2005), we estimated that about 15.4% of the sexually experienced participants in the absence of a HIV/STD risk-reduction intervention would test positive for CT, GC, or TV at either the 42-month or the 54-month follow-up. We estimated power for detecting significant differences in STD incidence over the follow-up period for attrition rates of 15% and 20% at the 54-month follow-up, $\rho = 0.009$, and STD incidence in the health-promotion control group = 0.154. At baseline, only 3.3% of participants were sexually experienced; hence, for the other 96% of participants, any STDs we detect will have been contracted during the follow-up period. The study is well powered to detect incidence differences in the range of at least 6.4% to 8.4%, depending on the true proportion of sexually experienced adolescents in the sample at the 54-month follow-up. Table 1 presents a range of estimates based on 38.3% to 76.5% of the baseline sample contributing to the STI incidence endpoint at the 54-month follow-up.

Table 1. Estimated power to detect a decrease in STD incidence assuming a cluster randomized controlled trial with a total of N=809, N=542, and N=405 sexually experienced participants enrolled from 18 matched pairs of schools (alpha = 0.05, two-tailed, rho = 0.009).

STD incidence			Attrition rate (54 months)					
			20%			15%		
Control	Intervention	Difference	N=809	N=542	N=405	N=809	N=542	N=405
0.154	0.10	0.054	0.76	0.58	0.47	0.78	0.61	0.49
0.154	0.09	0.064	0.88	0.73	0.60	0.90	0.75	0.63
0.154	0.08	0.074	0.95	0.84	0.72	0.96	0.86	0.74
0.154	0.07	0.084	0.98	0.91	0.81	0.99	0.93	0.84

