
Statistical Analyses. To address Hypothesis 1, we will use intervention type as the independent variable and model the incidence of sexual intercourse, unprotected sexual intercourse, and multiple partners as binary responses to test the effect of intervention using GEE on data collected preintervention and 3-, 6-, 12-, 42-, and 54-month follow-up.

Hypothesis 2 concerns whether the effects of HIV risk-reduction interventions may differ systematically among adolescents. Sexual experience, age, gender, intimate-partner violence, and sexual abuse history are the primary moderators of responsiveness to the HIV risk-reduction intervention we will consider. Although the notion that certain variables may moderate intervention effects is theoretically persuasive, little research has attempted to establish empirically the characteristics of intervention participants that might moderate the effectiveness of HIV risk-reduction interventions. Jemmott et al. (1998) found that a safer sex intervention was more efficacious with sexually inexperienced adolescents. We will test moderator effects using GEE, along the guidelines described by Baron and Kenny (1986) and Cohen and Cohen (1983). We will use GEE to test for significant interactions between intervention type and potential moderator, controlling for the main effects of all variables involved in the interaction. As an example, consider the moderation of intervention effects on intentions by age assessed as a continuous variable. By introducing an age-by-intervention interaction term, this moderation effect is easily tested using GEE.

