Hypothesis 3 concerns mediation of intervention effects. The theoretical framework underlying the intervention suggests that knowledge, perceived self-efficacy, behavioral beliefs, normative beliefs, and intentions should mediate the effects of the intervention on sexual-risk behavior. Mediation will be tested using a standard procedure described by Baron and Kenny (1986). To establish mediation, it is necessary to show that (a) the independent variable affects the dependent variable; (b) the independent variable affects the putative mediator; and (c) the mediator has a significant effect on the dependent variable when the independent variable is controlled. Within our context, the analyses will proceed as follows: we will test for statistical significance of the intervention's effect on sexual behavior. We will then test the effect on the potential mediators. Finally, we will test whether the potential mediators have significant effects on sexual behavior, controlling for intervention effects. This set of analyses will indicate whether the 3 criteria of mediation are met. If the intervention effect on sexual behavior outcomes is nonsignificant, these analyses would provide valuable information as to whether a

lack of effects on mediators may account for it. In addition, the analyses would establish whether the changes in the mediators predict reduced risk behavior, even if the intervention effects are nonsignificant. In this way, it will be possible not only to gain insight into the underlying mechanisms of behavior change, but also to test the theoretical framework that was used to guide the creation of the interventions.

To address Hypothesis 4, we will use intervention type as the independent variable and model the incidence of STD as binary response to test the effect of intervention using GEE on data collected at the 42- and 54-month follow-up.

2. Duration

Funded by the National Institute of Mental Health

Start date: April 1, 2002

End date: August 31, 2010

3. Subject Recruitment and Selection

The participants will be 1,057 6th grade Xhosa speaking South African adolescents recruited from 18 senior primary schools in Mdantsane and Berlin, Eastern Cape Province, South Africa. About 59 participants will be recruited from each of the 18 schools. On average, participants will range in age from 11 years to 14 years at baseline. About one-half of the adolescents will be female.

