STD infection rates among South African adolescents may place them at increased rates for sexually transmitted HIV infection. Although there is no national surveillance system for STDs in South Africa, a literature review estimated that 15% of family planning and antenatal clinic attendees were seropositive for syphilis, 16% had chlamydia (CT), and 8% had gonorrhea ([GC] Pham-Kanter et al, 1996). Johnson et al.'s (2005) recent review of 47 independent studies also revealed high STD prevalence among women attending antenatal and family planning clinics. The median estimated prevalence was 10% for syphilis, 11% for CT, 5% for GC, and over 20% for *Trichomonas vaginalis* (TV). STDs can increase the efficiency of sexual transmission of HIV (Fleming & Wasserheit, 1999; Grosskurth et al., 2000). Consistent with this, Pettifor et al.'s (2005) national survey of South Africans 15 to 24 years of age found that a history of STD symptoms was associated with HIV infection, and Auvert, [name] et al. (2001) tied biologically confirmed STDs to positive tests for HIV.

As in the US, STDs affect young people disproportionately. It is estimated that 4 million STD cases occur each year in South Africa, with over half of these infections occurring among adolescents and young adults (Dickson-Tettech & Ladha, 2000). Data from the 2000 antenatal clinic survey in the Eastern Cape revealed that young people 24 years of age and younger had the highest syphilis seropositive rate of any age group (Meidany & Puchert, 2001).

There are no national data on rates of CT, GC, or TV among South Africans 15 to 16 years of age. However, [name] (2007) of the CDC has provided relevant data from a study by Auvert, [name] et al. (2001) on youth in a township in the Carletonville district of the Gauteng Province, South Africa. That population-based, cross-sectional study used random sampling techniques to select households. Urine specimens were tested for CT and GC using ligase chain reaction assays. Although the article did not report results for adolescents 14 to 19 years of age separately, [name] provided us with the rates of these STDs in this sub-sample of 304 girls and

299 boys. The prevalence of CT was 9.9% and 3.7% in girls and boys, respectively. The prevalence of GC was 7.2% and 1.3% in girls and boys, respectively.

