Attached are copies of the female and male versions of the pre-intervention questionnaire, which were previously reviewed and approved by the IRB Committee. Compared with the female version of the questionnaire, the male version has only minor differences in a few questions (e.g., gender pronouns, boyfriend vs. girlfriend). Also attached is the questionnaire that will be used at the 42-month and 54-month follow-up.

Amendment to Study the Impact of Father Involvement on Xhosa Adolescents. This exploratory research seeks to collect information on the involvement of fathers in promoting HIV/STD risk reduction in their adolescent children. If the preliminary research suggests that interventions to help fathers reduce the health risks of their adolescent children are feasible and acceptable, then we would pursue additional research on father-child sexual risk reduction interventions in South Africa. We plan to conduct 8 focus groups with adolescents and parents of adolescents. All focus groups will be conducted in Xhosa and will be single-gender (all boys, all girls, all fathers, or all mothers). Two of each type of group will be conducted. Each group will last about 2 hours and will have about 10-12 participants. The focus groups will explore beliefs about fathers, father absence, father-adolescent relationships and communication, father involvement, the impact of fathers, why fathers might be absent, and ways of coping with father absence. They will also explore the impact of other males, including grandfathers and older brothers. The participants will complete a brief pre-focus group questionnaire before participating in the focus groups so that we can characterize the people who participated.

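### The Hypothesis 4 STD model names no covariates; prespecifying baseline gender and age would give a small gain in precision and robustness

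*Protocol*

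**What the plan says.** Section 1 of the Protocol, under Statistical Analyses, gives the Hypothesis 4 model in one sentence: "To address Hypothesis 4, we will use intervention type as the independent variable and model the incidence of STD as binary response", and then "to test the effect of intervention using GEE on data collected at the 42- and 54-month follow-up". No covariate is named and none is excluded.

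Both variables are available. Section 6 states "Attached are copies of the female and male versions of the pre-intervention questionnaire", so gender is recorded. The STD power paragraph in Section 1 reports "At baseline 76.54% of the adolescents in our study were 12 years or older", so age is recorded too. Section 3 expects a balanced sample: "About one-half of the adolescents will be female".

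Gender and age do have a role under Hypothesis 2: "Sexual experience, age, gender, intimate-partner violence, and sexual abuse history are the primary moderators of responsiveness". Those interaction models control for the main effects of the moderators. That text does not specify the Hypothesis 4 model.

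Section 5 gives sex-specific rates from an external survey, for ages 14 to 19: "The prevalence of CT was 9.9% and 3.7% in girls and boys, respectively" and "The prevalence of GC was 7.2% and 1.3% in girls and boys, respectively". Section 6 makes STD a secondary outcome, defined as any of CT, GC, trichomonas (TV) or HSV-2 at 42 or 54 months.

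**The concern.** A baseline variable that strongly predicts a binary outcome is normally worth including in the outcome model: it removes explained variation and guards against chance imbalance. On the protocol's own figures gender looks like such a variable for CT and GC. Age bears on who has become sexually active by 54 months, which is how the power section itself uses it.

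The design does not balance either variable. Section 1 pairs schools on the number of 6th grade learners, classrooms with electrical outlets and number of classrooms, with rural and urban schools paired separately. With 18 schools, the gender and age mix can differ between arms by chance. Attrition, optional specimens and the renewed consent for the long-term follow-up filter the tested sample further.

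At stake are a little precision on the trial's biological endpoint, and protection against having to choose between adjusted and unadjusted results after the data are seen.

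**Working it through.** **Inputs from the Protocol**
- CT 9.9% in girls and 3.7% in boys; GC 7.2% and 1.3% (Section 5).
- Control STD incidence 0.154; intervention incidence 0.10, 0.09, 0.08 or 0.07; at-risk N of 809, 542 or 405; attrition 20% or 15%; rho = 0.009; alpha = 0.05, two-tailed (Section 1, Table 1).
- 18 schools; about half the adolescents female (Sections 1 and 3).

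**Girl:boy ratios**
- CT: 9.9/3.7 = 2.68.
- GC: 7.2/1.3 = 5.54.
- CT and GC summed, ignoring co-infection: 17.1/5.0 = 3.42.

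**Assumptions**
- The composite outcome has a ratio r somewhere in 2.68 to 5.54. No TV or HSV-2 rate by sex is given.
- The at-risk sample is half female, and r is the same in both arms.
- Adjustment divides the effective sample size per arm by (1 − R²), where R² is the share of outcome variance that gender explains. The ICC is left unchanged.

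**The plan's own figure first.** For 0.154 v 0.09 at N = 809 and 20% attrition, Table 1 states power 0.88.
- Retained: 809 × 0.80 = 647, or about 324 per arm.
- Per school: 647/18 = 36.0. Design effect: 1 + (36.0 − 1) × 0.009 = 1.315.
- Effective n per arm: 323.6/1.315 = 246. Two-proportion power: 0.58.

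The stated 0.88 does not reproduce. Table 1 refers to 18 matched pairs where the design has 18 schools; reading it as 36 schools gives 0.64. This is a separate matter. Here 0.58 serves only as the base from which to measure the gain.

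**Variance explained by gender.** With arm incidence p, the boys' rate is b = 2p/(1 + r), the girls' rate is g = r × b, and the variance between the sexes is 0.25 × (g − b)². R² is the sum of this over both arms, divided by the sum of p(1 − p). For p = 0.154 and 0.09 the denominator is 0.1303 + 0.0819 = 0.2122.

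| r | Control g, b | Intervention g, b | R² |
|---|---|---|---|
| 2.68 | 0.224, 0.084 | 0.131, 0.049 | (0.0049 + 0.0017)/0.2122 = 0.031 |
| 3.42 | 0.238, 0.070 | 0.139, 0.041 | (0.0071 + 0.0024)/0.2122 = 0.045 |
| 5.54 | 0.261, 0.047 | 0.152, 0.028 | (0.0114 + 0.0039)/0.2122 = 0.072 |

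**Power after adjustment** (same cell, base 0.583)
- r = 2.68: effective n 246/(1 − 0.031) = 254; power 0.597.
- r = 3.42: effective n 258; power 0.603.
- r = 5.54: effective n 265; power 0.616.

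Across all the Table 1 scenarios at 20% attrition the gain is about 1 to 3 points.

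**Chance imbalance, for scale.** If pupils were allocated individually, the SD of the difference in gender share between arms would be sqrt(1/647) = 0.039 at N = 809, and sqrt(1/324) = 0.056 at N = 405. With the r = 3.42 gap of 0.169, an imbalance of 2 SD moves the STD difference by 2 × 0.039 × 0.169 = 1.3 points, or 2 × 0.056 × 0.169 = 1.9 points. Table 1 considers differences of 5.4 to 8.4 points. Schools are in fact randomised in pairs, and the document does not say how much gender mix varies between schools, so these SDs are only illustrative.

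**Age.** No STD rate by age is given, so no gain can be computed.

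**The case against.** A reader might infer that the protocol commits to a model with intervention type alone and so discards gender and age. The text does not support that. Calling intervention type the independent variable identifies the exposure under test, and the same phrase is used for Hypothesis 1. Covariates for a secondary outcome are commonly left to a statistical analysis plan, which may exist and is not shown. The Hypothesis 2 text shows that the investigators have both variables in view.

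A reader might also infer that the unadjusted comparison is biased. It is not. Under randomisation, chance imbalance is part of the sampling error that the test already allows for.

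The inputs are limited as well. The sex-specific rates are external and cross-sectional, are not restricted to sexually experienced adolescents, and cover two of the four STDs. Adjustment is not entirely free: with a logit link the odds ratio becomes conditional, and with 18 clusters each added parameter puts some further strain on robust standard errors.

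All of this stands, and it limits the point to a small one. It does not remove the point. Two covariates already in hand, at least one of them probably prognostic and neither balanced by the matching, would still bring a gain at little cost.

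**Conclusion.** The point holds as a minor improvement. The Hypothesis 4 model names no covariates, and adding baseline gender and age would make it slightly more efficient and more robust. Gender would explain about 3 to 7% of the outcome variance and add about 1 to 3 points of power. This rests on a girl:boy ratio of 2.7 to 5.5 for the composite, a sample that is half female, and an unchanged ICC. The size of any gain from age is unknown.

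The result should not be read as showing that the planned test is invalid. Nor would adjustment make up the gap between the recomputed power and Table 1, which is far larger than 3 points.

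**What to change.** In Section 1, Statistical Analyses, add to the Hypothesis 4 paragraph that the GEE will include baseline gender and age as covariates, that the adjusted intervention effect is the main result, and that the unadjusted effect will be reported alongside.

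The cost is one sentence and no new data. The text should state the link function: with a logit link the adjusted odds ratio is conditional on gender and age and is not directly comparable with the unadjusted one. Reporting both, each labelled for what it estimates, deals with this.

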Participation in Long-Term Follow-up. The participants will be told that the objective of the long-term follow-up continuation of the study is to determine the long-term efficacy of the interventions at 42 and 54 months after participation. They will be told that on two occasions over the course of two years they will complete questionnaires and provide urine and blood samples. They will be told that the questionnaires are similar to the questionnaires they previously completed in the study. They contain profoundly sensitive and personal questions, including personal questions about different sexual activities in which they may have engaged; drug, alcohol or birth control use; and previous STDs. They will be told that their answers will be confidential, that they will be given a code number, and that the data will be organized by their code number, not their name.

The participants will be told that the urine sample will be tested for three (3) STDs: chlamydia, gonorrhea, and trichomonas and that the blood sample will be tested for HSV-2. Participants will be informed (a) that STDs are commonly asymptomatic, (b) that if they test positive for an STD, they will be given single-dose treatment free of charge (c) that their parents will not be informed of the test results and (d) that they can choose not to provide blood and/or urine specimen(s). If the participant does not provide blood and/or urine specimen(s), they will remain in the survey room with the data collector while the other participants are giving their specimens. The risk and benefits of participation in the study will be explained. All participants will be told that participation is voluntary.

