The interventions differ in content, but are structurally similar. Adolescents will participate in a small group with 10 to 16 adolescents led by two specially trained Xhosa speaking adult co-facilitators. Intervention activities include small group discussions, interactive exercises, brainstorming, games, and role-playing designed to increase knowledge, motivation, and skill related to the behaviors that are the focus of the particular intervention.

Immediately after the last intervention session, the participants will attend a session to complete the Xhosa post intervention questionnaire. All participants will be contacted 3, 6, 12, 42, and 54 months post intervention and invited to complete the Xhosa follow-up questionnaire.

STD incidence. As a secondary outcome, we will examine Chlamydia trachomatis (CT), Neisseria gonorrhoea (GC), and Trichomonas vaginalis (TV) based on nucleic acid amplification tests on urine specimens and HSV-2 based on an ELISA test at 42-month and 54-month follow-ups. We will test the effects of the intervention on the presence of any of these four STDs at either the 42-month follow-up or the 54-month follow-up. We selected these STDs because of their high rates in this population and the availability of accurate tests for them. According to the World Health Organization (2001), CT is the most common bacterial cause of STD with an estimated 89 million annual cases worldwide, and GC is also common with over 60 million annual cases globally. However, the most common non-viral STD worldwide is caused by TV, with over 174 million estimated cases in 1999. Participants will go to the rest room and provide a first-void urine specimen of approximately 20 to 30 cc. Urine specimens will be refrigerated and delivered to the STI Reference Centre, National Institute for Communicable Diseases in Johannesburg within 28 days. A dedicated refrigerator at the project offices will be utilized for storing specimens exclusively before transporting them to the laboratory. A blood sample will be collected from each participant and shipped to the STI Reference Centre to be tested for herpes simplex 2 (HSV-2). [name] FRCP(UK) PhD, the Head of the STI Reference Centre, has agreed to serve as a co-investigator on the study to oversee the biospecimen collection, storage, shipping, and testing.

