We will employ Gen-Probe's Aptima combo assay for CT and GC and Aptima trichomonas vaginalis assay for TV. The sensitivity of Gen-Probe's tests for CT and GC and TV has been shown to be superior to culture and direct specimen tests. The greater sensitivity of the tests permits the use of specimens other than endocervical swabs for women and urethral swabs for men. It is the only assay with urine specimen sensitivity equivalent to swab specimen. An enzyme-linked immunosorbent assay (ELISA) test will be used to detect HSV-2 type specific IgG antibodies.

Clinical research coordinators will be trained to handle the biological specimens. A 2-day training will familiarize them with the follow-up study, train them in the details of their responsibilities, and emphasize the importance of confidentiality. Blind to the participants' original intervention condition, they will collect and handle the biological specimens and provide pre- and post-test counseling to participants. Participants will be notified of their test results, and detected CT, GC, and TV infections will be treated according to CDC guidelines. For both

ethical and methodological reasons, it is imperative that participants receive complete treatment. We will, therefore, treat participants with directly observable state-of-the-art single-dose oral therapy for these STDs to minimize potential non-adherence to multi-dose medication regimens.

[name] MBChB (UCT), MRCP DCH DA, a general practitioner and child development specialist who has a practice in East London, has agreed to serve as a Research Physician on the study to oversee the treatment of STDs and any follow-up care. She will be responsible for ensuring that those participants who test positive for chlamydia, gonorrhea, or trichomonas are treated according to CDC guidelines and that those who test positive for HSV-2 are referred for treatment and counseled. [name] will monitor the work of the Research Nurse who will dispense the medication to the participants who test positive for chlamydia, gonorrhea, or trichomonas and will refer participants as appropriate for additional follow-up care. [name] will order the medication that will be used to provide the single-dose treatment to STI positive participants as indicated in the protocol.

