Documentation of informed consent, including signed parent/guardian informed consent forms and adolescent assent forms, will be stored in a locked cabinet to which only authorized personnel have access.

9. Protection of Program Participants

The confidentiality of the information about participants will be maintained. No names or identifying information will be included in research reports. Participants' names will not appear on questionnaires. Participants' names will not appear on the biological specimens. Parents will not be informed of the results of the STD tests. Participants will be given code numbers and

information about them will be organized by code number--not name. The list of code numbers and names will be kept in a locked cabinet accessible only to authorized research staff.

We considered several factors in deciding against notifying parents of the adolescents' STD test results. If the adolescents believed that their parents would be told the results of their tests, the adolescents would be less likely to participate, which could bias the sample through self-selection. Parental notification does not concern protection of research participants, but parental rights. Adolescents who are tested have the opportunity to be treated for a potentially asymptomatic condition, whereas those who do not participate will not have this opportunity. This is a case where participation decreases risk.

10. Potential Benefits

Adolescents may learn about prevention of pregnancy and STDs, including HIV, or other major health risks of South Africans. They will learn ways to protect themselves from these health problems. They may enjoy participating since participants in similar projects have reported enjoying the interventions.

Adolescents will learn whether they have a STD, which may be asymptomatic. In South Africa, STD treatment is based on the presentation of symptoms, not screening. Thus, this study would provide a unique opportunity for the participants to have any asymptomatic STDs identified. STDs can cause pelvic inflammatory disease and infertility and are believed to be a co-factor in HIV transmission. They will receive treatment if they test positive. In addition, adolescents will be referred as appropriate for any mental health problems that become apparent during this research.

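### Participants are told that any positive STD test brings free single-dose treatment, but the study procedures provide this for three of the four infections tested and not for HSV-2

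*Protocol*

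**What the plan says.** Section 3 of the Protocol (Participation in Long-Term Follow-up) sets out what participants will be told before the 42- and 54-month visits. The statement on urine reads: "the urine sample will be tested for three (3) STDs: chlamydia, gonorrhea, and trichomonas". For the other specimen a single test is named, in the same sentence: "the blood sample will be tested for HSV-2". The next sentence lists four things they will be informed of. Item (b) is that "if they test positive for an STD, they will be given single-dose treatment free of charge". Item (d) is that they may decline to give blood, urine or both.

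Section 6 (STD incidence) describes what will be done. After listing the three urine infections and HSV-2, it says: "We will test the effects of the intervention on the presence of any of these four STDs". On treatment it says that "detected CT, GC, and TV infections will be treated according to CDC guidelines", and that participants will be treated with "directly observable state-of-the-art single-dose oral therapy for these STDs". The Research Nurse dispenses medication to those positive for chlamydia, gonorrhea or trichomonas. For the fourth infection the procedure is that "those who test positive for HSV-2 are referred for treatment and counseled".

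Section 10 (Potential Benefits) says of participants who learn that they have an STD: "They will receive treatment if they test positive".

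**The concern.** Item (b) in Section 3 makes three promises about a positive result: treatment is given, it is single-dose, and it is free. They apply to an STD without qualification, and HSV-2 has just been named as something to be tested for. Section 6 provides that package for three infections and a different pathway, referral with counseling, for HSV-2.

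What is at stake is the accuracy of the information on which an adolescent decides whether to give blood. Urine and blood can be refused separately, and the only test the Protocol states for the blood sample is HSV-2. The inaccurate promise therefore bears most directly on the specimen to which it does not apply. Section 9 adds weight to the treatment benefit: it cites the opportunity to be treated as part of its case for not notifying parents, and concludes that taking part lowers risk.

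**Working it through.** No arithmetic applies. The check sets the statements side by side for each infection.

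| Infection | Specimen (Section 3) | Counted as an STD (Section 6) | What participants are told (Section 3, item b) | What the study does (Section 6) |
|---|---|---|---|---|
| Chlamydia | Urine | Yes | Free single-dose treatment, given | Single-dose therapy, dispensed by the study |
| Gonorrhea | Urine | Yes | Free single-dose treatment, given | Single-dose therapy, dispensed by the study |
| Trichomonas | Urine | Yes | Free single-dose treatment, given | Single-dose therapy, dispensed by the study |
| HSV-2 | Blood | Yes | Free single-dose treatment, given (no exception stated) | Referral for treatment, and counseling |

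1. *Does item (b) reach HSV-2?* As worded, yes. It refers to a positive test for an STD, follows directly on a sentence naming the HSV-2 test, and contains no limiting word. Section 6 calls the set that includes HSV-2 "We will test the effects of the intervention on the presence of any of these four STDs", so the Protocol itself classes HSV-2 as an STD.

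2. *Does Section 6 provide single-dose treatment for HSV-2?* No. Treatment under the guidelines is stated for CT, GC and TV. The phrase about single-dose therapy points back to those three. The dispensing instruction names the same three, and HSV-2 has its own, different instruction. Section 6 does not say whether care obtained on referral is free.

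3. *Does any other passage reconcile the two?* None does. Section 6 provides pre- and post-test counseling and notification of results, but does not say that this counseling qualifies the treatment statement. Section 8, on consent and assent for the long-term follow-up, does not mention treatment by infection.

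4. *Is Section 10 a second conflict?* No. It promises treatment after a positive test, but does not say that it is single-dose, free or given by study staff. Referral for treatment is compatible with that sentence. It is imprecise, because a reader coming from Section 3 will take it in the same sense.

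By count, item (b) covers four of four infections and Section 6 delivers the described treatment for three of four. The remaining one is the only infection tested in blood.

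**The case against.** The strongest defence is that item (b) was meant only for the urine infections. Section 3 attaches the word STDs, with the number three, to the urine tests and names HSV-2 separately. Section 6 likewise uses "directly observable state-of-the-art single-dose oral therapy for these STDs" to mean CT, GC and TV. On this view item (b) is loose drafting and nobody intended to promise single-dose treatment for HSV-2. That may well explain how the sentence arose. It does not cure it: the limitation is not written, Section 6 counts four STDs, and an adolescent hearing the statement straight after the HSV-2 test is mentioned cannot be expected to supply the exception.

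Several stronger readings are tempting, and the documents do not support them:

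- *That HSV-2 positives are left without care.* They are not. Section 6 has them referred for treatment and counseled, and makes the Research Physician responsible for this.
- *That parents consent on a false statement.* Item (b) describes what participants are told. Parents receive their own consent form and letter, which Section 8 requires to be sufficiently informative. Those forms are not shown and may be correct.
- *That a positive participant will go on believing the infection has been dealt with, with a risk of onward transmission.* Participants are notified of results and receive pre- and post-test counseling, and HSV-2 positives are counseled and referred. A lasting misunderstanding is possible but is not shown. What stands is narrower: inaccurate information before the sample is given.
- *That Section 10 contradicts Section 6.* As shown above, it is compatible with referral for treatment.

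**Conclusion.** The point stands as an inconsistency between item (b) of the participant information in Section 3 and the procedure in Section 6. For HSV-2, one of the four infections tested, participants would be told of free single-dose treatment given to them, while the stated procedure is referral for treatment with counseling. Section 10 needs tidying on the same point but adds no second contradiction.

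In size, the statement reaches every participant asked for blood at the long-term visits. The 1,057 enrolled are only an upper bound, since attrition, the fresh consent and assent required by Section 8, and the right to decline blood all reduce it. The different pathway itself matters only for those who test HSV-2 positive, and the Protocol gives no expected number.

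The conclusion rests on reading item (b) as worded and on the Protocol alone. If the assent, consent and script texts already separate HSV-2 from the other three, the practical consequence shrinks to correcting the Protocol. The matter is one of participant information: no endpoint, sample size, power or analysis figure changes. No view is taken on which clinical handling is right.

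**What to change.** Reconcile item (b) of the long-term follow-up paragraph in Section 3 with the treatment paragraphs of Section 6, so that what participants are told about a positive result matches the stated procedure for each of the four infections, including who provides any treatment and whether it is free. The investigators must decide which of the two passages governs. Align the general sentence in Section 10 with the reconciled text. Then check the adolescent assent form, the parent or guardian consent form and cover letter, and the data collectors' standard script against it, and amend only those that differ.

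The cost is a wording amendment to a few sentences, with ethics review of any form that has to change, made before the text is next used with participants. No data collection, laboratory work or analysis is affected by the rewording.
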